7.7. Concomitant Therapy

All concomitant medications taken during the study must be recorded in the Concomitant Medication eCRF. All patients are encouraged to maintain their usual medication regimens for concomitant conditions or diseases throughout the study, unless those medications are specifically excluded ([Appendix 8](#)).

Patients taking permitted UC concomitant medications, other than oral corticosteroids, are to keep doses stable unless modifications are needed due to AEs, and follow the instructions regarding dose stabilization as detailed in [Appendix 9](#). Patients taking oral corticosteroids are to follow the corticosteroid taper instructions described below. Administration of prohibited UC medications, approved or investigational, constitutes treatment failure. Use of such medications should not be withheld if, in the opinion of the investigator, failure to prescribe them would compromise patient safety. Patients who require a prohibited medication to treat their UC (see [Appendix 8](#)) need to be discontinued from study drug and complete an ETV and post-treatment follow-up visits.

If a concomitant medication is needed to treat an AE or for appropriate medical management, the investigator should base decisions on the patient and clinical factors, considering prohibited medications. Local administration of corticosteroids (for example, intranasal, inhaled, intraarticular) are allowed as required for the management of pre-existing conditions and AEs. A patient who initiates a prohibited medication for a non-UC indication may either discontinue the study drug, or discontinue the prohibited medication.

Use of BCG vaccination is prohibited throughout the duration of the study and for 12 months after discontinuation of study drug. Use of nonlive (killed, inactivated or subunit) vaccinations are allowed for all patients; however, their efficacy with concomitant mirikizumab is unknown. Use of live, attenuated vaccines are prohibited during the study and for 3 months after discontinuation of study drug.

The list of prohibited medications and the list of permitted medications with dose stabilization guidance are provided in [Appendix 8](#) and [Appendix 9](#), respectively.

Corticosteroid Taper

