- Induction study responders who experience LOR and do not receive clinical benefit from mirikizumab IV rescue induction
- Induction study nonresponders who do not achieve clinical response with 3 doses of mirikizumab IV extended induction
- Induction study nonresponders who achieve clinical response with mirikizumab extended IV induction, but subsequently lose clinical benefit with open-label mirikizumab SC dosing, should be discontinued. Loss of clinical benefit may be based on demonstrating LOR criteria (see Section 5.1) or by other criteria according to investigator discretion
- Patients who require treatment with a prohibited UC medication ([Appendix 8](#)), an increase in immunomodulatory medication, or a course of corticosteroids that exceeds the baseline dose
- Patients who undergo surgery for UC

Safety Criteria for Study Drug Discontinuation

- The patient requires a prohibited medication to treat their UC ([Appendix 8](#)). A patient who initiates a prohibited medication for a non-UC indication may either discontinue the study drug, or discontinue the prohibited medication.
- The patient requires a colectomy, proctocolectomy, or partial colectomy during the study.
- A diagnosis of cancer, other than squamous cell or basal cell carcinoma of the skin, during the study.
- Dysplasia occurring in flat mucosa or DALM.
- A diagnosis of active TB during the study.
- A diagnosis of HIV/AIDS during the study.
- A diagnosis of hepatitis B during the study or development of detectable HBV DNA during the study (see Section [9.4.5.2](#)).
- A diagnosis of hepatitis C during the study or development of detectable hepatitis C virus (HCV) RNA during the study (see Section [9.4.5.4](#)).
- The patient becomes pregnant. Pregnant patients **will not** undergo an endoscopy at the ETV.
- The participant has an AE or SAE which, in the opinion of the investigator or sponsor, would preclude the participant from continuing to receive study drug.

- Systemic hypersensitivity event or anaphylaxis to study drug.

It is recommended that the patient be assessed by an appropriately trained professional to assist in deciding whether the patient is to be discontinued from the study if:

- The patient scores a 3 for Item 12 (Thoughts of Death or Suicide) on the Quick Inventory of Depressive Symptomatology—Self-Report (16 Items) (QIDS-SR16) at any time in the study, or
- The patient reports suicidal ideation or suicide-related behaviors during the study

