(North America/Europe/Other), (e) baseline value in the model, and (f) induction remission status. Type III sums of squares for LS means will be used for statistical comparison between treatment groups. The LS mean difference, standard error, p-value, and 95% CI, unless otherwise specified, will also be reported.

Any change to the data analysis methods described in the protocol will require an amendment ONLY if it changes a principal feature of the protocol. Any other change to the data analysis methods described in the protocol, and the justification for making the change, will be described in the clinical study report (CSR). Additional exploratory analyses of the data will be conducted as deemed appropriate.

10.3.1.1. Missing Data Imputation:

While every effort will be made to reduce missing data, the missing data imputation methods described below will be used to provide a conservative approach for assessing efficacy endpoints when patients are permanently discontinued from study drug or otherwise have missing data.

- Nonresponder imputation (NRI): For analysis of categorical efficacy and health outcomes variables, missing data will be imputed using an NRI method. Patients will be considered a nonresponder for the NRI analysis if they do not meet the categorical response criteria, have missing clinical response data at a time point of interest, or take rescue dosing with mirikizumab prior to the time point of interest.
- Mixed-effects model of repeated measures: For continuous variables, the primary analysis will be MMRM with the missing at random assumption for handling missing data. This analysis takes into account both missingness of data and the correlation of the repeated measurements. The data collected after rescue medication will be censored in the primary analysis. No additional imputation methods will be applied to the MMRM analysis.

Sensitivity analyses, including additional methods of handling missing data or analyzing the data that may be required to satisfy regulatory needs will be specified in the SAP.

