10.3.3. Efficacy Analyses

10.3.3.1. Primary Analyses

The primary endpoint is the proportion of patients with clinical remission at Week 40 (Week 52 of continuous therapy) among the patients who are responders to 300 mg mirikizumab IV at 12 weeks of induction dosing.

For study visits that include endoscopy as a study procedure (for example, Visit 11 [Week 40]), the SF and RB subscores of the Mayo score will be calculated from daily electronic diary data by averaging the most recent 3 valid days (possibly nonconsecutive) in the 7 days prior to commencing bowel preparation for endoscopy. At other study visits, where endoscopy is not performed, SF and RB subscores will be calculated from the daily electronic diary data by averaging the most recent 3 valid days (possibly nonconsecutive) in the 7 days prior to that study visit. If data for fewer than 3 valid days are available, the subscores will be considered missing. Patient diary data obtained on the following days will be excluded: (i) days when bowel preparation was taken prior to endoscopy, (ii) the day of the endoscopy, and (iii) the day after the endoscopy.

Rates of clinical remission at Week 40 among induction responders will be analyzed. Patients who do not achieve clinical remission or who do not reach the Week 40 assessment will be considered to be nonremitters. In addition, patients who take rescue dosing with mirikizumab will be considered nonremitters.

The primary endpoint analysis will utilize the CMH test as described in Section 10.3.1.

Additional analyses of the primary endpoint may be considered and will be fully detailed in the SAP.

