Appendix 8. Prohibited Medications

This section outlines medications that are prohibited during the treatment phase of the study, if applicable. Use of the medications listed in this appendix is allowed at the discretion of the investigator after a patient discontinues study drug and completes the early termination visit.

Drug Class	Comments
Anti-TNF antibodies (for example, infliximab, adalimumab, or golimumab)	Prohibited throughout treatment period
Anti-integrin antibodies (for example, vedolizumab)	Prohibited throughout treatment period
Agents depleting B or T cells (for example, rituximab, alemtuzumab, or visilizumab)	Prohibited throughout treatment period
Immunomodulatory medications, including oral cyclosporine, IV cyclosporine, tacrolimus, mycophenolate mofetil, thalidomide or JAK inhibitors (for example, tofacitinib)	Prohibited throughout treatment period
Rectally administered 5-ASAs (enemas or suppositories)	Prohibited throughout treatment period
Rectally administered corticosteroids (enemas or suppositories)	Prohibited throughout treatment period
Rectally administered investigational preparations for UC such as arsenic preparations	Prohibited throughout treatment period
Intravenous corticosteroids for UC	A course of IV corticosteroids for UC is prohibited
Systemic corticosteroids for non-UC indications (oral or IV)	Patients requiring systemic corticosteroids for non-UC conditions are excluded. Exceptions include corticosteroids to treat adrenal insufficiency, premedication for IP infusion, or locally administered corticosteroids (e.g., inhaled, intranasal, intra-articular, topical) (see Appendix 10)
Oral budesonide standard formulation (that is, not the oral budesonide extended release tablet formulation [budesonide MMX])	Prohibited throughout treatment period.
Any investigational therapy (biologic or nonbiologic)	Prohibited throughout treatment period
Interferon therapy	Prohibited throughout treatment period
Leukocyte apheresis (leukopheresis, for example, Adacolumn)	Prohibited throughout treatment period
Anti-IL12p40 antibodies (for example, ustekinumab [Stelara [®]]) or anti-IL-23p19 antibodies (for example, risankizumab [BI-655066], brazikumab [MEDI-2070], guselkumab [CNTO1959], tildrakizumab [MK-3222]) for any indication, including investigational use	Prohibited throughout treatment period

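### Section 7.7 calls prohibited UC medication treatment failure, but the nonresponder rules in 10.3.1.1 and 10.3.3.1 do not list it

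*Protocol*

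**What the plan says.** Section 7.7 (Concomitant Therapy) states without condition: "Administration of prohibited UC medications, approved or investigational, constitutes treatment failure". Later in the same paragraph, patients who require a prohibited medication for their UC "need to be discontinued from study drug and complete an ETV and post-treatment follow-up visits". Section 8.1.1 includes, among possible reasons for ending study drug, "Patients who require treatment with a prohibited UC medication". Appendix 8 allows the listed drugs only after study drug has stopped and the early termination visit (ETV) is done. Its list includes rectal 5-ASAs and rectal corticosteroids.

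Section 10.3.1.1 sets the nonresponder rule for categorical endpoints. A patient is a nonresponder if the response criteria are not met, or if they "have missing clinical response data at a time point of interest, or take rescue dosing with mirikizumab prior to the time point of interest". Section 10.3.3.1 sets the rule for the primary endpoint: "Patients who do not achieve clinical remission or who do not reach the Week 40 assessment will be considered to be nonremitters". It adds: "In addition, patients who take rescue dosing with mirikizumab will be considered nonremitters". Neither section names prohibited UC medication or refers to 7.7.

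The efficacy analysis uses the mITT population (10.2, 10.3.1), which keeps patients whether or not the protocol was followed.

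**The concern.** Section 7.7 attaches failure to an event, the taking of the drug. Section 10 attaches failure to a consequence expected to follow, absence of Week 40 data. The two agree only if the event always leads to discontinuation before Week 40.

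Where it does not, the primary outcome depends on what the site did rather than on what the patient took. Two patients with the same use of a prohibited UC drug and the same Week 40 findings could be classified differently because one was discontinued and the other was not. The second would be credited with a remission that 7.7 does not accept as treatment success.

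**Working it through.** **Setting the rules side by side**

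| Patient takes a prohibited UC drug and… | Section 7.7 | Section 10.3.3.1 |
|---|---|---|
| is discontinued before Week 40 | failure | nonremitter (Week 40 not reached) |
| continues and receives mirikizumab rescue | failure | nonremitter |
| continues, no rescue, not in remission at Week 40 | failure | nonremitter |
| continues, no rescue, in remission at Week 40 | failure | **remitter** |

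Only the last row conflicts. It can arise in these ways:

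- Section 7.7 ties failure to *administration*, but the discontinuation wording in 7.7 and 8.1.1 concerns patients who *require* the drug. Use that the site does not know about, or learns of late, meets the first and need not trigger the second.
- The 8.1.1 list is introduced as possible reasons. The instruction in 8.2 to stop before another effective agent is introduced sits under investigator decision.
- Rectal 5-ASAs or rectal corticosteroids could be taken without the site ending treatment.
- The last SC dose is at Week 36 (Table AMBG.7.1). For use that starts after it, no study-drug dose remains to be stopped before Week 40.

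**Reproducing the planned power**

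Inputs from Section 10.1: remission 47% on mirikizumab (n = 313) and 27% on placebo (n = 157), two-sided 0.05, chi-square test.

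- Pooled rate: (157 × 0.27 + 313 × 0.47)/470 = 0.4032
- SE under the null: √[0.4032 × 0.5968 × (1/157 + 1/313)] = 0.0480
- SE under the alternative: √[0.27 × 0.73/157 + 0.47 × 0.53/313] = 0.0453
- Power: Φ[(0.20 − 1.96 × 0.0480)/0.0453] = Φ(2.34) = 99.0%

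The stated power of more than 95% is correct. The planned relative risk is 0.47/0.27 = 1.74.

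**Leverage of a misclassified patient**

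The protocol gives no rate of prohibited-medication use, so the counts below are assumptions. Each case is a patient counted as a remitter on top of the planned rates. One placebo case raises that arm's rate by 1/157 = 0.64 points; one mirikizumab case raises that arm's by 1/313 = 0.32 points. The same power formula gives:

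| Assumed cases (mirikizumab + placebo) | Difference (points) | Power | Relative risk |
|---|---|---|---|
| 0 + 0 | 20.0 | 99.0% | 1.74 |
| 0 + 1 | 19.4 | 98.6% | 1.70 |
| 0 + 4 | 17.5 | 95.9% | 1.59 |
| 0 + 5 | 16.8 | 94.5% | 1.56 |
| 1 + 0 | 20.3 | 99.2% | 1.75 |
| 6 + 0 | 21.9 | 99.7% | 1.81 |
| 2 + 1 | 20.0 | 99.0% | 1.72 |
| 6 + 3 | 20.0 | 98.9% | 1.69 |

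Exact enumeration of the chi-square test gives the same power to within 0.2 percentage points. Cases in proportion to arm size leave the difference unchanged but lower the relative risk, which 10.3.1 says will be reported.

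**The case against.** The best defence is that the rules agree whenever the protocol is followed. Sections 7.7, 8.1.1 and 8.2 and Appendix 8 all point to stopping study drug, and a patient who stops early does not reach Week 40. An ETV is not the Week 40 assessment, so endoscopy done there should not restore remission status. On this view the remaining cases are protocol deviations, handled by the per-protocol repeat and by the SAP. The amendment rationale in Appendix 12, useful only as evidence of intent, shows that reliance on missing data was deliberate. It could also be said that treatment failure in a concomitant-therapy section is not an endpoint definition.

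Much of this stands: the affected group is narrow, and the size is unknown. It does not remove the conflict:

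- The per-protocol repeat does not reclassify anyone in the mITT primary analysis.
- What 10.3.1.1 and 10.3.3.1 leave to the SAP is sensitivity and additional analyses. The primary trigger list is fixed in the protocol, so an SAP that follows it conflicts with 7.7, and one that adds the trigger departs from Section 10.
- Use after the last dose at Week 36 need not involve a failure to stop dosing.
- The Appendix 12 rationale expects these patients to be nonresponders because their data will be missing. That reasoning gives no answer when the data are observed.

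**Conclusion.** The concern holds. The current text classifies the same patient as a treatment failure in 7.7 and as a remitter in 10.3.3.1 when a prohibited UC drug is taken, study drug is not discontinued, no mirikizumab rescue is given and remission is observed at Week 40. The same gap affects the other categorical endpoints through 10.3.1.1.

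The effect on the result is probably small, and its direction depends on which arm has more such cases. Placebo cases dilute the observed effect and mirikizumab cases inflate it. With the planned rates and arm sizes, power stays above 95% for up to four placebo-only cases. The case for correction is therefore consistency of the primary outcome definition, not a shortfall in power. Confidence is moderate, because no frequency is available and the SAP is not at hand.

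**What to change.** Add one sentence to each of 10.3.1.1 and 10.3.3.1: a patient who takes a medication prohibited by Appendix 8 for the treatment of UC before the time point of interest is a nonresponder (nonremitter), whether or not data are observed. Refer to 7.7 in both places. Limiting the rule to use for UC keeps it clear of non-UC use, which 7.7 handles separately. This concerns outcome classification only; the prohibited list, discontinuation rules and rescue treatment are unchanged.

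The cost is two sentences and possibly slightly lower response rates. Most of the data are already required: "All concomitant medications taken during the study must be recorded in the Concomitant Medication eCRF". The protocol does not say that the indication is captured on that form; this is assumed here and should be confirmed, since the rule depends on it.

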10.3.1.2. Multiplicity Control

A prespecified multiple testing scheme based on graphical approach (Bretz et al. 2009, 2011) will be used to test the primary and major secondary hypotheses at overall family wise type 1 error rate (FWER) of 0.05. The graphical approach is a closed testing procedure; hence, it strongly controls the FWER across all endpoints (Alosh et al. 2014). Details of the specific graphical testing scheme (including testing order, interrelationships, type I error allocation for the major secondary endpoints, and the associated propagation) will be prespecified in the SAPs prior to first unblinding of efficacy.

10.3.2. Treatment Group Comparability

10.3.2.1. Patient Disposition

The number of enrolled patients will be summarized by cohort and by treatment. Frequency counts and percentages of all patients who are enrolled and complete the study or discontinue the

study drug/study early will be presented. Reasons for discontinuing the study drug/study will be summarized.

10.3.2.2. Patient Characteristics

Year of birth, sex, weight, smoking habits, prior biologic therapy, and other demographic and disease characteristics will be summarized for all enrolled patients. Age and body mass index will be calculated. Demographic and baseline disease characteristics will be summarized for each treatment group and by cohort. Certain characteristics, such as weight, that are collected after baseline, will be reported as a listing.

10.3.2.3. Concomitant Therapy

Concomitant therapy will be collected at each visit, and the reported term will be classified by the World Health Organization drug dictionary. Medications started prior to randomization and medications started on study after randomization will be presented separately in frequency tables by drug name and by cohort for all enrolled patients.

Patients who are noncompliant will be listed by treatment and by cohort. The details of noncompliance will be defined in SAP. A contingency table of numbers of noncompliant patients by treatment and by cohort will be provided.

10.3.3. Efficacy Analyses

10.3.3.1. Primary Analyses

The primary endpoint is the proportion of patients with clinical remission at Week 40 (Week 52 of continuous therapy) among the patients who are responders to 300 mg mirikizumab IV at 12 weeks of induction dosing.

For study visits that include endoscopy as a study procedure (for example, Visit 11 [Week 40]), the SF and RB subscores of the Mayo score will be calculated from daily electronic diary data by averaging the most recent 3 valid days (possibly nonconsecutive) in the 7 days prior to commencing bowel preparation for endoscopy. At other study visits, where endoscopy is not performed, SF and RB subscores will be calculated from the daily electronic diary data by averaging the most recent 3 valid days (possibly nonconsecutive) in the 7 days prior to that study visit. If data for fewer than 3 valid days are available, the subscores will be considered missing. Patient diary data obtained on the following days will be excluded: (i) days when bowel preparation was taken prior to endoscopy, (ii) the day of the endoscopy, and (iii) the day after the endoscopy.

Rates of clinical remission at Week 40 among induction responders will be analyzed. Patients who do not achieve clinical remission or who do not reach the Week 40 assessment will be considered to be nonremitters. In addition, patients who take rescue dosing with mirikizumab will be considered nonremitters.

The primary endpoint analysis will utilize the CMH test as described in Section 10.3.1.

Additional analyses of the primary endpoint may be considered and will be fully detailed in the SAP.

10.3.3.2. Secondary Analyses

The secondary efficacy and health outcome endpoints of the trial are presented in [Table AMBG.4.1](#) and details of the analysis methods that will be utilized are provided in Section [10.3.1](#).

The endpoints for the major secondary objectives will be analyzed using the similar CMH test used for the primary endpoint. Multiplicity adjustment for type 1 error control to the major secondary endpoints is described in Section [10.3.1.2](#).

Additional analyses of the secondary efficacy and health outcome endpoints may be considered and will be fully detailed in the SAP.

10.3.3.3. Exploratory Analyses

Details of the analysis of exploratory endpoints will be fully detailed in the SAP. Additional analyses of exploratory health outcome endpoints may be considered and will be fully detailed in the SAP.

10.3.4. Safety Analyses

Safety will be assessed by evaluating exposure, AE (for example, treatment-emergent AE [TEAE], SAE, treatment related AE, discontinuation due to AE), AESI (for example, infection, MACE, injection site event, hypersensitivity event, etc.), laboratory analytes, vital signs, ECGs, C-SSRS, etc.

Adverse events will be coded according to the Medical Dictionary for Regulatory Activities and summarized by system organ class, preferred term, severity, and relationship to investigational product. A TEAE is defined as an event that first occurred or worsened in severity after baseline, which is the on-study AE recorded at Week 12 in the induction study. For each event classification term, the number of patients experiencing a TEAE with that classification term will be tabulated.

The safety analyses for the main cohort will compare mirikizumab to placebo during the maintenance treatment. For other cohorts, the safety data will be summarized without treatment comparison.

The Fisher exact test will be used to perform the between-treatment group comparisons for AEs, discontinuations, and other categorical safety data. The change from baseline in continuous vital signs, physical characteristics, and other continuous safety variables, including laboratory variables, will be summarized by visit and treatment. The change from baseline to last observation value will be analyzed with the ANOVA model with baseline as a covariate. The last non-missing observation in the treatment period will be used as the last observation.

Shift tables for categorical safety analyses (for example, “high” or “low” laboratory results) will also be produced.

